#### **4.7 Lost to Follow-up**

Long-term safety assessment of subjects treated with a gene therapy product is a regulatory requirement and every effort will be made to continue monitoring long-term subject safety. If a subject is lost to follow-up, every effort should be made to contact the subject's Primary Care Practitioner or General Practitioner, with the subject's consent, to obtain information on the subject's status.

#### **4.8 Long-term Follow-up**

All subjects who receive treatment with GT005, including those that have withdrawn from the study for any reason, will, subject to consent, be enrolled in a separate long-term follow-up study (ORACLE). The long-term follow-up study will evaluate the long-term safety and durability of GT005 after the final follow-up visit at Week 96 or early termination visit. Any unresolved AEs from this study will be monitored until the event has resolved, subsided or stabilised in the long-term study. If a subject does not agree to participate in the long-term follow-up study, any ongoing AEs will be followed until the event has resolved, subsided or stabilised.

## 5 STUDY TREATMENT

GT005 is a recombinant, non-replicating AAV2 expressing human CFI.

### 5.1 Acquisition and Accountability

GT005 is supplied to the surgical site.

The Investigator, or designee (e.g., Pharmacist), will ensure that all GT005 is stored in a secured area, under recommended temperature monitored storage conditions, in accordance with applicable regulatory requirements and will be dispensed by qualified staff members who have been designated as unmasked.

For Part 1, the designated unmasked study member(s) is (are) responsible for GT005 accountability, reconciliation, and record maintenance throughout the study. Accountability records must be maintained throughout the course of the study and these must be available for inspection by the Study Monitor during the study. Masking to the doses in Part 1 will be maintained at the site level (subjects, masked site personnel and masked monitors) until the end of the study. For Part 2, designated unmasked study member(s) is (are) not required.

All expired GT005 should be recorded in the accountability records and will be destroyed locally, as per local guidelines once final accountability is completed. Details regarding the handling and preparation of GT005 are detailed in the Pharmacy Manual.

### 5.2 Formulation, Appearance, Packaging and Labelling (include comparator information)

GT005 is supplied to the surgical site as a vial of frozen sterile liquid. GT005 is an aqueous suspension of recombinant AAV2 vector particles in [REDACTED]

[REDACTED] GT005 will be labelled in accordance with the appropriate Competent Authority regulations.

### 5.3 Product Preparation, Storage, and Dispensing

GT005 post-administration measures regarding disposables are detailed in the Pharmacy Manual.

[REDACTED] GT005 should be handled as per the Pharmacy Manual.

#### 5.4 Dosing and Administration

GT005 will be assessed at two doses; low dose (████ vg) and high dose (████ vg) in Part 1; and low dose █████ vg) in Part 2.

GT005 is administered as a single-time subretinal injection into the study eye of subjects allocated to one of the two GT005 doses. The surgical procedure for subretinal administration of GT005 is based on standardised methodology. It is conducted by a qualified Vitreoretinal Surgeon in an operating room under local anaesthesia. Other anaesthetic options may be considered by the Surgeon as appropriate for the subject. The detailed procedure is described in the Surgical Manual.

Subjects allocated to GT005 treatment are injected with GT005 across a minimum of one or more bleb(s) following the procedure below:

[REDACTED]  
[REDACTED]  
[REDACTED]  
[REDACTED]  
[REDACTED]

Subjects allocated to the untreated control group will not receive any treatment.

#### 5.5 Measures to Minimise Bias: Randomisation and Masking

This is an open label, outcomes assessor-masked study. In Part 1, the Sponsor, Investigators, subjects, study personnel involved in the study will remain **dose-masked** to those randomised to GT005.

In Part 2, the Sponsor, Investigators, subjects, and study personnel performing clinical assessments will be **unmasked** to dose received, since only the low dose will be administered.

In order to minimise the potential impact of knowledge of treatment, the randomisation list will be kept strictly confidential, such that no aggregate statistical analyses by efficacy across the study by treatment shall be performed prior to the database lock/interim analysis (as applicable), except for those specified in the DMC charter review for the closed sessions.

For Part 1 only, unmasked study personnel will be assigned to prepare GT005 for administration; however, they will not be involved in any other aspect of the study (i.e., consent, safety/efficacy assessments, surgical procedure).

To minimise bias, all imaging endpoint assessments and grading will be performed at a CRC. All imaging efficacy assessments are to be performed in a fully-masked fashion. █████

The randomisation process is defined in Section 3.4.

Additional measures to minimise bias include standardised methodologies across participating sites, and similar visit/assessment schedule for treated/untreated subjects.

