### 6.1.3 Visit 2, Day 1 (Surgical Site)

Visit 2 will only apply to subjects randomised to GT005.

This visit will be performed at a centralised surgical site and will be split in three parts: pre-surgery, surgery, and post-surgery assessments.

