#### 6.1.3.3 Post-surgery – Day 2 (Surgical Site)

The following assessments are required one day post-surgery:

- Concomitant medication

■ [REDACTED]

- Vital signs

- AEs/

- Ophthalmic examination

■ [REDACTED]

- OCT macula

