#### 6.1.4 Day 3 (Telephone call)

Day 3 telephone call will only apply to subjects randomised to GT005.

The following information will be recorded:

- Concomitant medication

■ [REDACTED]

- AEs

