#### 6.1.5 Visit 3 (Week 1) (Surgical Site)

Visit 3 (Week 1) will only apply to subjects randomised to GT005.

The following assessments will be performed:

- Concomitant medication

■ [REDACTED]

- AEs

- Vital signs

- Ophthalmic examination

- BCVA using ETDRS

- OCT macula

■ [REDACTED]

- OCT-A and/or FA if clinically indicated (if a subject converts to wet AMD)

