#### 6.1.7 Visit 4, Week 5 (Local or Surgical Site for GT005 Subjects/Telephone Call for Untreated Control Subjects)

At Week 5, subjects may choose to attend a local investigative site or surgical site for clinical assessments and ophthalmic imaging, with review of images by both the local site Investigator and the Surgeon.

Subjects allocated to untreated control will receive a telephone call from their local investigative site to review concomitant medications and AEs.

Visit 4 (Week 5) assessments listed below will only apply to subjects randomised to GT005.

The following assessments will be performed:

- Concomitant medication
- [REDACTED]
- Vital signs
- AEs
- Biochemistry/haematology
- [REDACTED]
- Ophthalmic examination
- OCT macula
- [REDACTED]
- BCVA using ETDRS
- CFP
- FAF
- OCT-A and/or FA if clinically indicated (if a subject converts to wet AMD)
- [REDACTED]
- [REDACTED]
- [REDACTED]

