#### 6.1.8 Visit 5, Week 8 (Local or Surgical Site)

Visit 5 (Week 8) assessments listed below will only apply to subjects randomised to GT005:

- Concomitant medication
- AEs
- Ophthalmic examination
- [REDACTED]
- BCVA using ETDRS
- OCT-A and/or FA if clinically indicated (if a subject converts to wet AMD)

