### **2.7.1 Adverse events (AEs)**

Only AEs that occurred during the study period (from the date of randomization to the end of study) will be summarized. AEs recorded after screening but before the date of randomization will be listed only.

**Treatment-emergent Adverse Event (TEAE):** An adverse event is considered treatment emergent if the start date/time of the event is on or after the date of randomization, irrespective of the treatment arm. The primary summaries of AEs will be based on TEAEs.

The number (and percentage) of subjects with AEs will be summarized separately for ocular (study eye and fellow eye) and non-ocular events by treatment group in the following ways unless otherwise specified:

- Overall summary of death, subjects with any AE, any severe AE, any study treatment-related AE, any surgical procedure related AE, any AE leading to study discontinuation, any serious AE (SAE), any study treatment-related SAE, any surgical procedure related SAE, any SAE leading to study discontinuation
- AEs by primary SOC and PT
- AEs related to study treatment by SOC and PT (separately for study eye and non-ocular)
- AEs related to surgical procedure by SOC and PT (separately for study eye and non-ocular)
- SAEs by primary SOC and PT

- SAEs related to study treatment by SOC and PT (separately for study eye and non-ocular)
- SAEs related to surgical procedure by SOC and PT (separately for study eye and non-ocular)

A subject with multiple adverse events within a primary SOC is only counted once towards the total of the primary SOC.

All AEs, deaths, and SAEs (including those from the pre- and post-treatment periods) will be listed and those collected after the use of alternative GA therapies/medications, or during the pre-treatment, post-study period will be flagged. In addition, subjects who are not receiving treatment due to surgical procedure-related AEs will be listed separately by treatment group.

The MedDRA version used for reporting the AEs will be described in footnote.

For the legal requirements of ClinicalTrials.gov and EudraCT, two required tables on “on-treatment/treatment emergent” adverse events which are not serious adverse events with an incidence greater than 2% (or other cutting point as appropriate) and on “on-treatment/treatment emergent” serious adverse events and SAE suspected to be related to study treatment will be provided by system organ class and preferred term on the safety set population (i.e., the FAS of this study).

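### Protocol 5.5 names similar schedules as a bias control, but they match only from Week 12; unequal early ascertainment can inflate GT005 non-ocular and fellow-eye AE percentages

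*Protocol*

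**What the plan says.** Protocol 5.5 closes its list of measures against bias with standardised methods across sites and a "similar visit/assessment schedule for treated/untreated subjects".

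The visit sections describe different early schedules:
- **Day 1** (6.1.3): "Visit 2 will only apply to subjects randomised to GT005".
- **Day 2** (6.1.3.3), part of the same GT005-only visit: "The following assessments are required one day post-surgery", followed by a list that includes AEs and an ophthalmic examination.
- **Day 3** (6.1.4): "Day 3 telephone call will only apply to subjects randomised to GT005".
- **Week 1** (6.1.5): "Visit 3 (Week 1) will only apply to subjects randomised to GT005".
- **Week 2** (6.1.6): a call, again for GT005 only.
- **Week 5** (6.1.7): a clinic visit for GT005. For control, "Subjects allocated to untreated control will receive a telephone call from their local investigative site to review concomitant medications and AEs".
- **Week 8** (6.1.8): the "assessments listed below will only apply to subjects randomised to GT005".

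From Week 12 both arms attend at Weeks 12, 24, 36, 48, 72 and 96.

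SAP 2.7.1 counts an AE as treatment-emergent from the date of randomisation in both arms and summarises to the end of study. Numbers and percentages of subjects are "summarized separately for ocular (study eye and fellow eye) and non-ocular events by treatment group". It specifies no split by time of onset and no summary restricted to visits that both arms share.

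**The concern.** The frequency of treatment-emergent AEs is a named secondary endpoint, and the untreated arm is its only comparator. Subjects and sites know the allocation. Early study-eye events in GT005 are expected after intraocular surgery and raise no difficulty here. Non-ocular and fellow-eye events are different, because the control percentage is the natural yardstick for them.

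A subject who is asked seven times in twelve weeks will tend to report more minor, self-limiting events than one who is asked once. Raised intraocular pressure in the fellow eye or an abnormal laboratory value may never be recorded if nobody looks. Any such difference pushes the GT005 percentage upward. A reader who relies on 5.5 would believe that contact frequency had been balanced and could take an early excess as an effect of treatment.

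**Working it through.** **Contacts, counted from Protocol Tables 1 and 2 and Section 6.1**

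| After the randomisation call | GT005 | Control |
|---|---|---|
| AE contacts before Week 12 | 7 (Days 1, 2, 3; Weeks 1, 2, 5, 8) | 1 (Week 5 call) |
| AE contacts, Week 12 to Week 96 | 6 | 6 |
| Total AE contacts | 13 | 7 |
| Ophthalmic examinations before Week 12 (both eyes, Protocol 7.3.1) | 4 (Day 2; Weeks 1, 5, 8) | 0 |
| Laboratory draws before Week 12 | 1 (Week 5) | 0 |

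Day 1 is counted as one contact. Counting pre-surgery and surgery separately makes 8. Adding the randomisation call, which both arms receive, gives 8 v 2 before Week 12.

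**Size of the effect on self-reported events**

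The plan states no AE rate or recall figure, so there is nothing of its own to reproduce. Assume the same constant true event rate in both arms, and that an event is reported at the next scheduled contact with probability 0.5^(lag/h), where h is the recall half-life. A gap of L weeks between contacts then yields D(L) = (h/ln 2) × (1 − 0.5^(L/h)) effectively observed weeks. The recorded rate ratio is ΣD(GT005)/ΣD(control).

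For h = 4 weeks, h/ln 2 = 5.771:
- GT005, Weeks 0 to 12, gaps 1/7, 1/7, 5/7, 1, 3, 3, 4: ΣD = 9.437.
- Control, Weeks 0 to 12, gaps 5, 7: ΣD = 3.344 + 4.055 = 7.400 (rounded after summing).
- Ratio = 9.437/7.400 = 1.28.
- Weeks 12 to 96, both arms, gaps 12, 12, 12, 24, 24: ΣD = 3 × 5.049 + 2 × 5.681 = 26.509.
- Ratio over 96 weeks = (9.437 + 26.509)/(7.400 + 26.509) = 35.946/33.909 = 1.060.

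| h (weeks) | Mean detection, Weeks 0–12 | Ratio | Mean detection, Weeks 0–96 | Ratio |
|---|---|---|---|---|
| 2 | 0.64 v 0.42 | 1.53 | 0.229 v 0.201 | 1.137 |
| 4 | 0.79 v 0.62 | 1.28 | 0.374 v 0.353 | 1.060 |
| 8 | 0.88 v 0.78 | 1.14 | 0.554 v 0.540 | 1.025 |
| full recall | 1 v 1 | 1.00 | 1 v 1 | 1.00 |

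The percentage of subjects with at least one recorded event is 1 − exp(−λ ΣD). Suppose 50% truly have such an event by Week 12, so that λ = −ln(0.5)/12 = 0.0578 per week. At h = 4:
- To Week 12: 42.0% v 34.8%, a gap of 7.2 points (10.6 at h = 2; 4.2 at h = 8).
- To Week 96: 87.5% v 85.9%, a gap of 1.6 points (4.7 at h = 2; 0.4 at h = 8).

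These figures cover self-reported events only. Findings that depend on an examination or a blood test are outside the model.

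**A second early asymmetry**

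The treatment-emergent clock starts at randomisation in both arms. Control Day 1 is the next day, but GT005 Day 1 is the day of surgery. Protocol 6.1.2 places randomisation inside a screening-to-surgery interval of up to 8 weeks (12 by agreement). With a gap of x weeks, full recall and a true 12-week probability p, the extra time adds [1 − (1 − p)^((12+x)/12)] − p to a 12-week percentage. For p = 0.25 and x = 4 this is (1 − 0.75^(16/12)) − 0.25 = 6.9 points. Over assumed x of 2 to 8 weeks and p of 10% to 40% it runs from 1.6 to 17.3 points. This can exceed the recall effect and has nothing to do with contact frequency.

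**The case against.** The other side has several good points.

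- **The wording of 5.5.** It says similar, not identical, and does not mention AEs. The text before it concerns masking and central reading of images. For the primary imaging endpoint, both arms have autofluorescence at the same post-baseline visits apart from one early GT005 image that the amendment history describes as a safety assessment. This stands for efficacy. It does not make 7 contacts against 1, or 4 examinations against none, similar.
- **Look-back questioning.** Protocol 7.4.2 asks about the whole period since the previous visit, Section 8 also accepts spontaneous reports, and Section 5.6.1 requires routine fellow-eye monitoring in both arms. With full recall the self-report gap vanishes. This stands, and it makes the size a matter of assumption.
- **Dilution.** SAP 2.7.1 tabulates the whole study, not the first twelve weeks, so the larger ratios do not apply to its tables. This also stands. The 96-week figures are the relevant ones for a subject with full follow-up; a subject who leaves earlier sits nearer the 12-week ratio.
- **Consequence.** The extra visits are post-operative monitoring and are shown openly. The AE tables are descriptive, Protocol 9.4.2 plans no inferential testing, and the SAP introduction says development has stopped. This limits the importance of the point but does not correct the sentence.

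A reader might infer that GT005 percentages will be higher through ascertainment alone. The documents do not support that. They contain no recall or AE rate data, and surgery, anaesthesia, corticosteroids and the randomisation-to-surgery interval act in the same weeks.

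**Conclusion.** The statement in Protocol 5.5 is contradicted by the protocol's own schedules before Week 12, and SAP 2.7.1 has nothing that would let a reader see the consequence. Unequal ascertainment can inflate GT005 non-ocular and fellow-eye AE percentages. Under the assumed 2 to 8 week recall half-life and equal true rates, the inflation is modest over the reported period: a rate ratio of 1.025 to 1.14, or about 0.4 to 4.7 points if half of subjects truly have such an event by Week 12. In Weeks 0 to 12 the ratio is 1.14 to 1.53. Full recall gives no self-report gap. Events found only by examination or laboratory test are not quantified.

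A reader might also conclude that between-arm statements should rest only on events after Week 12. That goes too far. It would set aside the perioperative weeks, when systemic effects of surgery and its medication are most plausible. It would also discard early serious AEs (SAEs), which have a 24-hour reporting duty and for which no bias has been shown. The point is a low-cost improvement to wording and presentation.

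**What to change.** 1. **Protocol 5.5.** Limit the statement to Week 12 onward, for example: visit and assessment schedules are the same in both arms from Week 12; before Week 12, GT005 subjects have additional post-operative contacts and examinations.
2. **SAP 2.7.1.** Keep the whole-period tables. Add tables of non-ocular and fellow-eye AEs by onset: randomisation to Day 1; Day 1 to the Week 12 visit; after the Week 12 visit. The first period is needed because a split starting at Day 1 would drop GT005 events between randomisation and surgery. State how GT005 subjects who never reach surgery, and so have no Day 1, are assigned.
3. **Table note.** Say that contacts and examinations are matched between arms only in the last period, so a between-arm difference in the earlier periods should not be read as a treatment effect alone.
4. **Safety statements.** Do not restrict SAE or perioperative safety statements to the later period. Leave the study-eye tables as they are.

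The cost is one wording change and one extra set of tables, with fewer events in each period. No new data are needed, because AE onset dates are already collected and the SAP already has rules for partial ones. Nothing in the visit schedule changes.

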## 5.6 Concomitant Medication/Therapy Rescue Medication

### 5.6.1 Required/Permitted Medication

During the course of the study, subjects will be allowed to continue taking all prescribed and non-prescribed medications, unless specified in the exclusion criteria (see Section 4.2) and Section 5.6.2 Prohibited Medication. If the fellow (non-study) eye requires treatment for GA, it may be treated at the discretion of the investigator. Fellow eye treatment will be captured in the eCRF. The fellow eye must be monitored according to routine clinical practice and AEs captured in the eCRF.

Prior to administering the corticosteroid therapy, Investigators must refer to relevant Summary of Product Characteristics and/or label guidance for use. [REDACTED]

- [REDACTED]
- [REDACTED]
- [REDACTED]
- [REDACTED]
- [REDACTED]
- [REDACTED]

Note that AREDS based supplements are permitted as no effect on progression of GA has been reported.

Concomitant medications will be checked throughout the study and any change in medication after the date on which the subject signs the informed consent should be recorded in the eCRF.

### 5.6.2 Prohibited Medication

There are no contraindicated medications for GT005 treatment. Potential subjects who previously received a gene/cell-based therapy at any time are excluded.

The treatments displayed in Table 3 below are not allowed after Visit 1 (screening).

**Table 3: Prohibited Medications for Study Eye Only**

Medication	Prohibition period for GT005 arm	Prohibition period for untreated control arm	Action taken
Investigational GA medication	Week 96	Week 96	Record in eCRF and continue with study visits until end of study
Approved GA medication	Week 96	Week 48	Record in eCRF and continue with study visits until end of study

### **5.7 Treatment of Overdose of GT005**

In the event of overdosing of GT005, the site personnel must document and report the error to the overseeing Investigator. In the event of inflammation, subjects should be treated with corticosteroids (see Section [5.6.1](#)).

### **5.8 Administration Compliance**

The product is delivered as a single-time administration by subretinal injection. The subretinal injection is undertaken by a qualified and trained Vitreoretinal Surgeon at a centralised surgical site. The Investigator at the surgical site is responsible for ensuring GT005 is handled in accordance with the protocol and is only administered to subjects enrolled into the study that are allocated to received GT005 through IRT.

## 6 STUDY PROCEDURES

The schedule of observations and assessments during the study are summarised in [Table 1; Table 2] for subjects allocated to GT005 and subjects allocated to the untreated control, respectively. As treatment assignment will not be known until randomisation, the screening assessments listed in the schedule of assessments are the same in both tables.

Subjects enrolled at local investigational sites and randomised to GT005 may be invited to travel to a conveniently located surgical site for treatment and immediate post-operative follow-up visits only as summarised in [Table 1].

### Definition of Local Site versus Surgical Site

Local investigational sites are defined as sites that are approved to participate in this clinical study, but require identified subjects to be transferred for surgery. Subject consent, screening, and post-operative follow-up visits will be conducted according to the visit schedule outlined in schedule of assessments [Table 1] and [Table 2].

Surgical sites are defined as sites that are approved to participate in this clinical study and also approved to perform the surgical procedure as part of this clinical protocol. If a subject is screened at the Surgical Site, all assessments will be performed at this site.

Following successful screening and randomisation, pre- and post-surgical assessments should be performed at the Surgical Site for all subjects randomised to GT005. Subjects will complete the remainder of assessments at the Local Site as per the schedule of assessments [Table 1] and [Table 2].

### 6.1 Study Visits

#### 6.1.1 Screening (Visit 1: Local or Surgical Site)

##### Genotyping Visit

Subjects entered into the study must have genotyping and serum CFI evaluation performed by a Sponsor-approved laboratory, either through participation in another Gyroscope sponsored study or during the EXPLORE screening period. Subjects being considered for inclusion (who have not been previously genotyped in a Gyroscope sponsored study) will be required to provide a consent, agreeing to provide a sample for genetic testing or permit the analysis of an existing sample for this EXPLORE protocol. Following subject consent, samples will be collected and shipped to a central laboratory for genotyping. Samples will be used for genetic testing for variants relating to AMD.

**For Part 1 only:** Where prior genotyping has been performed on subjects as aforementioned, and the subject is shown to carry a CFI rare variant that meets inclusion requirements, then the complete screening visit (Visit 1) can take place.

If a subject has been genotyped at an alternative laboratory and shown to carry a CFI rare variant that meets inclusion requirements, then the complete screening visit (Visit 1) can take place, however an additional sample for confirmation of genotype must be taken at this time to confirm the finding. A separate informed consent form (ICF) will be used to obtain permission to perform the confirmation of genotype. This consent may be performed and obtained remotely, if required. The subject may not continue past Visit 1 until genetic confirmation has been obtained.

For those subjects who have not previously been genotyped, and who fulfil Inclusion Criteria 1, 2, and 3, consent for genotyping and a genotyping sample should be obtained prior to performing any other screening assessments (Visit 1). A separate ICF will be used to obtain permission to perform the genotyping. This consent may be performed and obtained remotely, if required. The subject can then proceed to perform the remaining screening assessments once genetic confirmation has been obtained.

Where necessary, and to facilitate the completion of all screening assessments, Visit 1 can occur over a number of days.

